11.2 Sample Size Considerations

Using a ratio of 1:1, a sample size of 27 subjects per treatment group (54 subjects total) provides 80% power to detect a treatment reduction in TSS AUC of at least 55% from placebo (assuming TSS AUC from the previous Phase 2a clinical challenge study to: mean [standard deviation]) of placebo: 500 [450] and EDP-938: 225 [200]) using a t-test with unequal variance. Assuming a 20% dropout rate, approximately 35 subjects per treatment group (approximately 70 subjects total) are needed.

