11.6.2 Secondary Efficacy Analyses

Sensitivity analysis of the primary endpoint will be performed using the Markov Chain Monte Carlo (MCMC) method of multiple imputation (*Dong and Peng, 2013*). Following imputation using MCMC methods, the TSS AUC will be calculated and an ANCOVA model with treatment group and stratification factor as fixed effects, and the baseline TSS as a covariate will be performed. Treatment groups will be compared using a type III sum-of-squares. Other sensitivity analysis may include a mixed model repeated measures analysis on the change from Baseline over all visits.

The RSV RNA viral load AUC measured in nasopharyngeal swab samples by RT-qPCR will be measured on Days 1, 3, 5, 9, and 14. The trapezoid rule will be used to calculate the AUC of the RSV RNA viral load. An ANCOVA model with treatment group and stratification factor as fixed effects and the baseline RSV RNA viral load as a covariate will be performed. Treatment groups will be compared using a type III sum-of-squares. The proportion of subjects with RSV RNA below the lower limit of quantitation will be analyzed on Days 3, 5, 9, and 14. Treatment groups will be compared using a Cochran-Mantel-Haenszel test controlling for the stratification factor.

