#### 2.2.2 Secondary Endpoints

- AUC from Day 1 through Day 14 for RSV RNA viral load measured in nasopharyngeal swab samples by quantitative reverse transcription polymerase chain reaction (RT-qPCR)

- Percentage of subjects with RSV RNA viral load below the limit of detection on Days 3, 5, 9 and 14 respectively
- Plasma PK concentrations of EDP-938 and its major metabolites (EP-024636, EP-024594, and EP-024595) on Days 1, 3 and 5
- Safety endpoints include, but are not limited to, AEs, vital sign measurements, pulse oximetry measurements, and clinical laboratory test results (including chemistry, hematology, and urinalysis)
- Time to RSV RNA viral load below the limit of detection
- RSV RNA viral load and change from baseline over time

[REDACTED]

[REDACTED]

[REDACTED]

[REDACTED]

[REDACTED]

[REDACTED]

[REDACTED]

[REDACTED]

[REDACTED]

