### 3.4 Treatment Assignment/Randomization

Subjects will be randomized to a treatment group using an Interactive Web Response System (IWRS). Subjects will be randomized in a 1:1 ratio to the EDP-938 or placebo treatment group as shown below:

- Treatment Group 1 (approximately 35 subjects): 800 mg of EDP-938 orally once daily for 5 days
- Treatment Group 2 (approximately 35 subjects): Placebo orally once daily for 5 days

In addition, subject randomization will be stratified based on the presence or absence of asthma/COPD.

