### 3.5 Analysis Populations

Subjects will be initially diagnosed using a local rapid antigen test. A central laboratory RT-PCR assay will be used to confirm the local results.

*Safety (SAF) Population:* All subjects who receive at least one dose of study drug. Subjects will be analyzed in the treatment group that corresponds to the study drug received during the study.

*Modified Intent-to-Treat (mITT) Population:* All randomized subjects positively diagnosed using the central RT-PCR test who receive at least one dose of assigned study drug will be included in the mITT population. The mITT population will be considered the efficacy population. Subjects will be analyzed as randomized.

*Per Protocol (PP) Population:* All subjects in the mITT population who completed 5-day treatment period and do not have major protocol deviations that may unduly influence TSS. Protocol deviations that would exclude subjects from the PP population are defined in *Section 3.8 (Protocol Deviations)*. Subjects will be analyzed as randomized.

*Pharmacokinetic (PK) Population:* All subjects receiving active study drug and having any measurable plasma concentration of study drug at any timepoint.

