The proportion of subjects with RSV RNA viral load below the limit of detection (LOD) will be analyzed on Days 1, 3, 5, 9, and 14, respectively. Treatment groups will be compared at each visit day using a Cochran-Mantel-Haenszel test controlling for the stratification factors of asthma/COPD status (present or absent). Additionally, the number and proportion of subjects with RSV RNA viral load below LOD will be summarized for each treatment group, and their respective 95% CIs will be reported based on the normal approximation. The adjusted difference in proportions between the 2 treatment groups will be computed as a weighted average of the treatment differences across strata using the Mantel-Haenszel weights, and the associated 95% CI will be provided using the Sato variance estimator (Sato, 1989).

[figure not shown]
Time to RSV RNA viral load below LOD will be analyzed using a Cox Proportional Hazards model. Stratification factors, baseline RSV RNA viral load and asthma/COPD status (present or absent), will be included. For calculating time to RSV viral load below LOD it is required of at

least two consecutive timepoints (or end of study) with viral load below LOD. Time to RSV viral load below LOD will be defined as the time between the date of first dose to the first date of achieving viral load below LOD, of the two consecutive timepoints or end of study. Subjects who discontinue early and subject who do not achieve viral load below LOD will be censored at the end of study date reported on the End of Study CRF. A Kaplan-Meier curve will display the probability estimates of achieving RSV RNA viral load below LOD. Descriptive statistics on the graph will include the median and 95% confidence interval at a minimum.

Descriptive statistics will be displayed for RSV RNA viral load and change from baseline by visit (Days 1, 3, 5, 9 and 14) and will include at a minimum the number of non-missing measurements, mean, standard deviation, median, minimum, 25th percentile, 75th percentile, maximum, and 95% CI for the mean.

Line graph of RSV RNA viral load will be produced:

- (1) Observed mean viral load  $\pm$  95% confidence interval by days (1, 3, 5, 9 and 14) for each treatment group

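### The normal-approximation CIs for the per-arm proportion below LOD collapse to zero width at 0/n or n/n (expected on Day 1) and are unreliable near those extremes; the SAP names no fallback

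*SAP*

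**What the plan says.** SAP 3.14.2 summarises the number and proportion below LOD in each arm and states that "their respective 95% CIs will be reported based on the normal approximation". No formula is given, and the visible text names no exact or score alternative for extreme counts. The only clause on insufficient data, in SAP 3.1, concerns keeping the asthma/COPD factor in models.

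The same section says the proportion "will be analyzed on Days 1, 3, 5, 9, and 14, respectively". Day 1 is not an endpoint day elsewhere. SAP 2.2.2 lists "Percentage of subjects with RSV RNA viral load below the limit of detection on Days 3, 5, 9 and 14 respectively", and Protocol 11.6.2 says "The proportion of subjects with RSV RNA below the lower limit of quantitation will be analyzed on Days 3, 5, 9, and 14". (The protocol's threshold is the quantitation limit and the SAP's is the detection limit. That is a separate matter and does not affect this point.)

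Efficacy analyses use the mITT population, which SAP 3.5 defines as "All randomized subjects positively diagnosed using the central RT-PCR test who receive at least one dose of assigned study drug". The plan is about 35 subjects per arm (SAP 3.4), based on 27 per arm before the allowance for dropout (Protocol 11.2).

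**The concern.** The normal approximation for a single proportion is weakest with small samples and proportions near 0 or 1. The arms here are small. The Day 1 proportion is pushed towards 0 by the population definition, and an antiviral trial that samples from early infection to Day 14 could meet either extreme at other visits.

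At stake is the honesty of the error bars printed beside each proportion. A table could show 0% (0%, 0%), which reads as certainty, or a limit below 0% or above 100%. If no method is named in advance, any replacement would be chosen after the output has been seen.

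**Working it through.** **Sample size, to fix n.** Protocol 11.2 assumes TSS AUC means (SD) of 500 (450) and 225 (200), and an unequal-variance t-test.

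- Standard error at 27 per arm: √[(450² + 200²)/27] = √(242,500/27) = 94.8.
- Noncentrality: 275/94.8 = 2.90, with Satterthwaite df 35.9. Two-sided power at alpha 0.05 is 0.806, so the stated 80% reproduces.
- With 20% dropout: 27/0.8 = 33.75, rounded up to 34. The plan says about 35.

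The check therefore uses n = 35 and n = 27.

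**Formulas**, with p = x/n and z = 1.96:

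- Wald: p ± z√[p(1−p)/n].
- Wilson: {p + z²/(2n) ± z√[p(1−p)/n + z²/(4n²)]} / (1 + z²/n).
- Clopper-Pearson: exact binomial limits.

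**Zero width.** At x = 0 or x = n, p(1−p) = 0, so the Wald interval is a single point for any n. At x = 0 the Wilson upper limit is z²/(n + z²): 3.84/38.84 = 9.9% at n = 35 and 3.84/30.84 = 12.5% at n = 27.

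**Impossible limits.** The Wald lower limit is negative when 0 < x < n·z²/(n + z²), which is 3.46 at n = 35 and 3.36 at n = 27. So counts of 1, 2 and 3 are affected at both sizes. By symmetry, counts of n−3 to n−1 give upper limits above 100%.

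| Count | Wald, % | Wilson, % | Clopper-Pearson, % |
|---|---|---|---|
| 0/35 | 0 to 0 | 0 to 9.9 | 0 to 10.0 |
| 1/35 | −2.7 to 8.4 | 0.5 to 14.5 | 0.1 to 14.9 |
| 34/35 | 91.6 to 102.7 | 85.5 to 99.5 | 85.1 to 99.9 |
| 0/27 | 0 to 0 | 0 to 12.5 | 0 to 12.8 |
| 3/27 | −0.7 to 23.0 | 3.9 to 28.1 | 2.4 to 29.2 |
| 27/27 | 100 to 100 | 87.5 to 100 | 87.2 to 100 |

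**Coverage.** For a true proportion p, coverage is the sum of the binomial probabilities of every x whose interval contains p. The chance of a zero count is (1−p)ⁿ. The documents give no expected proportions, so p runs over an assumed range; values for 1−p are the mirror image.

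| True p | Wald coverage, n = 35 / 27 | Wilson coverage, n = 35 / 27 | Chance of zero count, n = 35 / 27 |
|---|---|---|---|
| 0.02 | 51% / 42% | 97% / 90% | 49% / 58% |
| 0.05 | 83% / 75% | 97% / 96% | 17% / 25% |
| 0.10 | 87% / 94% | 92% / 95% | 2.5% / 5.8% |
| 0.12 | 93% / 84% | 94% / 96% | 1.1% / 3.2% |
| 0.18 | 88% / 87% | 95% / 95% | 0.1% / 0.5% |
| 0.30 | 92% / 93% | 94% / 94% | under 0.1% |
| 0.50 | 96% / 95% | 96% / 95% | under 0.1% |

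Most of the loss at very low p is the zero count itself: [0, 0] can never contain a positive p. Between about 10% and 20%, Wald coverage is erratic because the counts are discrete. Clopper-Pearson stayed at or above 95% at every p tried.

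**Day 1.** If both arms are 0/n, the Cochran-Mantel-Haenszel (CMH) statistic is 0/0 and cannot be computed. The Sato variance was checked in two illustrative strata, with 28 and 7 subjects per arm: with both arms at 0/n or both at n/n, the difference is 0 and its interval is [0, 0].

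**The case against.** The strongest reply is that the one occurrence tied to the documents is harmless and the rest is hypothetical.

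- **Day 1 is a pre-dose baseline.** A count near zero there reflects the mITT definition, not treatment, so no efficacy reading depends on that interval. The zero count is itself an inference. SAP 3.5 does not say which central assay confirms RSV, and no section says that it shares a detection limit with the viral-load RT-qPCR. A few Day 1 values below LOD are possible.
- **On Days 3 to 14 nothing points to extreme proportions.** At the tabulated values of 30% and 50%, Wald coverage is 92–96%. At 20% with n = 35, its mean width slightly exceeds Wilson's (25.9 against 25.4 percentage points).
- **The wording leaves room.** No Wald formula is written, parts of SAP 3.1 are redacted, and the table shells are a separate document.
- **Nothing inferential uses these intervals**, and the count is printed beside them.
- **Wilson is not perfect:** 89.9% at n = 27, p = 0.02, and 92.0% at n = 35, p = 0.10.

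Much of this stands, and it is why the point is minor. It does not remove the defect. Day 1 counts of 1–3 instead of 0 would give negative limits. Wald is the natural reading of the text. A named method should also hold at counts the trial may well produce. Wilson's dips are far smaller than Wald's at the same low proportions.

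**Conclusion.** The concern holds. On the Wald reading, zero width at 0/n and n/n is algebra and needs no further assumption. Limits outside 0–100% at counts of 1–3 and n−3 to n−1 follow directly at n = 27 and n = 35. The coverage loss is large for true proportions below about 5% or above about 95%, at 83% / 75% or worse (n = 35 / 27). It is irregular between 5% and 20% (and the mirror range), and mostly a few points in the middle.

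This rests on three assumptions: that the normal approximation means Wald, that the visible text is complete on this point, and, for Days 3 to 14, that extreme proportions may occur. That Day 1 will be at or near zero is inferred from the mITT definition.

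The consequence is confined to descriptive per-arm intervals of a secondary antiviral endpoint. The primary TSS AUC analysis, the CMH test and the Mantel-Haenszel difference with its Sato interval do not use them. The change is worth making but not essential.

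**What to change.** In SAP 3.14.2:

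1. Replace the normal approximation for the per-arm 95% CIs with the Wilson score method at every visit where a CI is shown. Use Clopper-Pearson instead if coverage of at least 95% is wanted.
2. Report Day 1 as count and percentage only, with no CI and no CMH test, so that the analysed days match the endpoint days 3, 5, 9 and 14 in SAP 2.2.2 and Protocol 11.6.2.
3. Keep the CMH test and the Mantel-Haenszel/Sato difference on those four days. Add a footnote that the Sato interval also has zero width if both arms are 0/n or both n/n, and must not then be read as precision.

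The cost is one phrase, one list of days, one footnote and one SAS option, with no new data. The price is wider intervals at extreme proportions: at n = 35 and p = 0.05 the mean widths are 12.6 (Wald), 15.8 (Wilson) and 16.9 (Clopper-Pearson) percentage points. In mid-range Wilson is slightly narrower than Wald (31.0 against 32.6 at n = 35, p = 0.5), with the same coverage. The change should be made before unblinding.

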On Day 3 and Day 5 (EOT), subjects should bring their study drug with them as part of their study site visit [REDACTED] for drug accountability and for dosing of study drug on Day 5 as described in [Section 5.7](#). If a subject is unable to attend the Day 3 and/or Day 5 study site visit, a home visit by a study nurse may be arranged, if feasible; refer to the SPM for details. It is anticipated that every reasonable effort will be made to ensure that subjects return to the site for the Day 3 and Day 5 visits.

Subjects who discontinue treatment early (ie, prior to completing 5 days of dosing) should return to the study site within 24 hours and no more than 48 hours later to complete the EOS procedures.

All study assessments during the Treatment Period are detailed in the SoA ([Appendix 1](#)).

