11. STATISTICAL CONSIDERATIONS

11.1 General Considerations

Statistical analysis of this study will be the responsibility of Enanta Pharmaceuticals, Inc. or its designee. Details of the statistical analysis methods will be described in the statistical analysis plan (SAP) document.

Continuous endpoints will be summarized using n, mean, standard deviation, median, 25th quartile, 75th quartile, minimum, and maximum values. Categorical endpoints will be summarized by the number of subjects meeting the endpoint and the percentage of subjects out of the appropriate population. The denominator will be displayed when needed. Statistical inference will be performed as appropriate. Inferential testing will be conducted using a two-sided alpha of 0.05, unless stated otherwise.

Any change to the data analysis methods described in the protocol will require an amendment if it changes a principal feature of the protocol. Any other change to the data analysis methods described in the protocol, and the justification for making the change, will be described in the clinical study report or SAP. Changes may only be made in the SAP prior to unblinding.

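### As written, SAP 3.14.2 censors every early leaver in the time to RSV RNA below LOD, including those who already have a confirmed clearance

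*SAP*

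**What the plan says.** Time to RSV RNA below LOD is a secondary endpoint (SAP 2.2.2). SAP 3.14.2 analyses it with a Cox model and a Kaplan-Meier curve.

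- **Event.** The SAP requires "at least two consecutive timepoints (or end of study) with viral load below LOD". The event is dated to the first of the two swabs, or to end of study.
- **Censoring.** "Subjects who discontinue early and subject who do not achieve viral load below LOD will be censored at the end of study date", that date being the one on the End of Study CRF.
- **Early leavers' last swab.** Under Protocol 7.1.2, subjects who stop treatment early "should return to the study site within 24 hours and no more than 48 hours later to complete the EOS procedures". Protocol 7.1.3 asks the same of those who leave the study early. The end-of-study column of the Schedule of Assessments includes the viral-load swab.

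Neither document says which sentence takes precedence when a subject has met the event definition and then leaves. Protocol 11.6.2 has no time-to-event rule that would settle it.

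**The concern.** The repeated subject in the censoring sentence makes two separate groups: those who discontinue early, and those who never reach LOD. The first group is not restricted to subjects without an event. A programmer who follows the sentence removes clearances that the preceding sentences have just defined as events.

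This does more than lose information. A subject who has cleared the virus stays in the risk set as though still positive until leaving. If EDP-938 speeds clearance, its leavers are more likely to have cleared before they go, so the rule removes more events from that arm and pulls the hazard ratio towards 1. If the arms differ in how many leave, withdrawal alone can move the hazard ratio.

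**Working it through.** **1. The only dropout figure in the documents.** Protocol 11.2 states: "Using a ratio of 1:1", "a sample size of 27 subjects per treatment group (54 subjects total) provides 80% power", with "placebo: 500 [450] and EDP-938: 225 [200]) using a t-test with unequal variance". Alpha is two-sided 0.05 (Protocol 11.1: "Inferential testing will be conducted using a two-sided alpha of 0.05, unless stated otherwise").

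- SE = √(450²/27 + 200²/27) = √8981.5 = 94.8
- Noncentrality = 275/94.8 = 2.90, Satterthwaite df = 35.9
- Power = 80.6% at 27 per group (79.0% at 26), so the plan's figure reproduces.
- "Assuming a 20% dropout rate, approximately 35 subjects per treatment group": 27/0.8 = 33.75, so 34 per group, within rounding of the stated 35.

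This calculation serves the primary endpoint. No event count, hazard ratio or power is stated for time to clearance. The useful input is 20% dropout: 0.20 × 70 = 14 possible early leavers, 7 per arm.

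**2. The two sentences applied to the same subject.**

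| Early leaver's swabs | Event definition | Censoring sentence |
|---|---|---|
| Below LOD Days 5 and 9, leaves Day 10 | Event, Day 5 | Censored |
| Below LOD Days 3 and 5, EOS swab Day 7 | Event, Day 3 | Censored, Day 7 |
| Positive Day 3, below LOD Day 5 and at EOS Day 7 | Event, Day 5 | Censored, Day 7 |
| Positive Days 3 and 5, below LOD at EOS Day 7 | Depends on the meaning of end of study | Censored, Day 7 |

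The first two rows conflict however end of study is read. The third needs only that the EOS swab counts as a timepoint.

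**3. Size when EDP-938 works.** Assumed, not in the documents: exponential clearance with medians of 5 days (EDP-938) and 8 days (placebo) after first dose, no isolated negative swabs, swabs on Days 3, 5, 9 and 14, leaving uniform over Days 3 to 13 with an EOS swab 1 to 2 days later, 20% leaving each arm, 35 per arm, Cox model with Efron ties. A hazard ratio above 1 favours EDP-938.

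| Rule | Events | HR | Power |
|---|---|---|---|
| Confirmed clearances kept | about 48 | 1.61 | 36% |
| All early leavers censored | about 42 | 1.54 | 27% |

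Hand check, using SE(log HR) ≈ √(4/events):

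- Kept: ln 1.61/√(4/48) = 0.476/0.289 = 1.65; Φ(1.65 − 1.96) = 38%
- Censored: ln 1.54/√(4/42) = 0.432/0.309 = 1.40; Φ(1.40 − 1.96) = 29%

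Both are close to the simulated values. The loss is 6/48 = 12.5% of events, or about 6 of the 14 leavers.

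Other assumptions give smaller losses. With 10% isolated negative swabs, HR goes from 1.50 to 1.45 and power from 28% to 24%. With a true HR of 1.5 and a placebo median of about 8 days after a one-day shift, events go from 47.0 to 41.5, HR from 1.52 to 1.49 and power from 27% to 24%.

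**4. Size when there is no effect** (median 7 days in both arms, all early leavers censored).

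| Dropout | HR | Type I error |
|---|---|---|
| 20% vs 20% | 0.99 | about 3–4% |
| 25% vs 15% | 0.91 or 1.10 | about 4–6% |
| 30% vs 10% | 0.80 or 1.26 | about 12% |

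The HR falls below 1 when EDP-938 loses more subjects and rises above 1 when placebo does. For the 30% versus 10% split, type I error ranged from about 6% to 13% across variants of the assumptions. Keeping confirmed events in that split gives HR 0.99 to 1.04 and about 5%.

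**5. The end-of-study clause.** With confirmed events kept and equal dropout, counting a single negative at any EOS visit or only at Day 14 gives HR 1.60 versus 1.61. Under the second set of assumptions in step 3, mean events are 48.7 versus 47.0.

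**The case against.** The strongest reply is that censoring ordinarily applies only to subjects without an event, that the definition comes immediately before, and that the sentence is merely ungrammatical. That may well be the intent, and a careful programmer might do the right thing unprompted. But the text does not say so, and its grammar points the other way, so the objection lowers the stakes without removing the point.

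Three stronger readings are tempting, and the documents do not support them.

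- *The end-of-study clause contradicts the censoring rule by making one negative early EOS swab an event.* This is an ambiguity, not a demonstrated contradiction. SAP 1 places the EOS Visit on Day 14, SAP 3.1 ties completion to Day 14 ± 1, and the viral-load windows in SAP 3.6 have no early-termination row. Those support the narrow reading. The schedule's footnote on early leavers permits the wider one without requiring it. With equal dropout the choice barely moves the result.
- *The rule inflates type I error.* Not with equal dropout. Protocol 11.2 gives one overall 20% and no difference between arms. Inflation to about 12% needs an assumed threefold imbalance.
- *The reading could be picked to suit the result.* Protocol 11.1 allows SAP changes only before unblinding, and nothing in the documents suggests otherwise.

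It is also fair that this is one secondary endpoint among several. Viral-load AUC and the proportion below LOD by visit do not use this rule.

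**Conclusion.** The point holds. Followed as written, the censoring sentence discards clearances that meet the SAP's own event definition. The dependable cost, under the assumed medians of 5 and 8 days with 20% leaving each arm, is about 6 of 48 events, a hazard ratio of about 1.54 instead of 1.61, and power of about 27% instead of 36%. Under the other assumptions tried, the power loss was 3 to 4 points. Bias under the null needs unequal dropout and becomes material only when the imbalance is large. Clearance times, leaving times and any dropout split are all assumptions, and the simulated Cox model compares arms without the SAP's covariates. The primary analysis and the sample size are untouched.

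**What to change.** Reword SAP 3.14.2 before unblinding to state that:

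1. A subject with two consecutive swabs below LOD has an event on the date of the first of them, whether or not the subject later discontinues.
2. Only subjects without a qualifying event are censored.

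Two clarifications belong in the same edit, although they have little numerical effect:

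- whether the end-of-study exception covers only the scheduled Day 14 (±1) swab or also an early EOS swab;
- whether early discontinuation here means stopping treatment or leaving the study. SAP 3.7 tabulates the two separately, and both lead to EOS procedures.

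The cost is SAP wording and the matching derivation. No new data, visits or subjects are needed. If the exception is limited to Day 14, about one unconfirmed event per arm is given up.

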7.1.3 Follow-up Period (Days 6 to 14)

Study Site Visits (Days 9 and 14):

Subjects should return to the study site for follow-up visits on Day 9 and Day 14 (EOS Visit) for post-treatment safety assessments. Visit assessments may be completed at the study site or by a study nurse via a home visit, if feasible; refer to the SPM for details.

Subjects who discontinue the study early (ie, prior to Day 14) should return to the study site within 24 hours and no more than 48 hours later to complete the EOS procedures.

All study assessments during the Follow-up Period are detailed in the SoA ([Appendix 1](#)).

Throughout the study, safety for each subject in each study period will be evaluated by assessment of clinical laboratory findings, physical examination findings (as applicable), vital sign measurements, pulse oximetry measurements (only for subjects with asthma or COPD), and AEs. Any subject with ongoing AEs/SAEs at the EOS Visit should be followed up until resolution of their AE/SAE or until the Investigator has determined that the event has stabilized as discussed in [Section 9.3](#).

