7.2.2 Procedures for Early Discontinuation or Early Termination of Treatment

Subjects who prematurely discontinue treatment early and have received at least one dose of study drug should return to the site within 24 hours and no more than 48 hours later and undergo the EOS procedures per the SoA ([Appendix 1](#)). Any subject who withdraws with ongoing AEs/SAEs should be followed up until resolution of their AE(s) or until the Investigator has determined that the AE(s) has stabilized.

Site staff will attempt to contact any subject who does not return to the site for the EOS Visit at least three times using the subject's preferred method of communication, followed by a letter requiring delivery notification if the three attempts were unsuccessful. Any subject who still cannot be reached following those attempts will be considered lost to follow-up. These subjects will be included in the PK and safety analysis as indicated in [Section 11.3](#).

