### 3.14.2 Secondary Efficacy Analyses

The RSV RNA viral load will be measured in nasopharyngeal swab samples by quantitative reverse transcription polymerase chain reaction (RT-qPCR) on Days 1, 3, 5, 9 and 14. Viral load values reported as TD (Target Detected, but below LLOQ) will be set to the average of LOD (limit of detection) and LLOQ (lower limit of quantification). Viral load values reported as TND (Target Not Detected, below LOD) will be set to zero. Viral load data will be transformed using a log10 scale before analyses. In case of zero value, the log transformed value will be also set as zero.

There will be two readings for both RSV A and RSV B, one from each of the two wells (i.e. A1, A2, B1, and B2). In case of any technical failure, no readings will be reported for the standard test, but a re-test will be done using a different aliquot from the same sample to produce valid results. PPD's unblinded statistician will then review the data and identify samples meeting discrepancy criteria for RSV A or RSV B. For these samples, a re-test will be performed using a different aliquot from the same sample. The discrepancy criteria for RSV A (same for RSV B) are defined as the following:

- Both A1 and A2 are numeric, and A1/A2 is  $>10$  or  $<1/10$  (i.e., one log difference);
- One of A1 and A2 is numeric, and the other one is TD or TND
- One of A1 and A2 is TD, and the other one is TND

For each sample, the final data will contain one or two sets of results.

The final RSV value (for A and B separately) for each sample will be the simple mean of the readings in original scale based on the following:

- Two readings from the only set if the final data have only one set of results.
- Two readings from the set without discrepancy if the final data have two sets of results and one set has discrepancy while the other set has no discrepancy
- Four readings from both sets if the final data have two sets of results and both sets have discrepancy
- Four readings from both sets if the final data have two sets of results and both sets have no discrepancy

Note: The readings reported as TND (target not detected) will be replaced by zero and those reported as TD (target detected) will be replaced by the average of LOD and LLOQ in the calculation of the RSV value.

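### Time to RSV RNA below LOD is censored at the End of Study CRF date rather than the last swab, which understates clearance for subjects who leave without an end-of-study swab

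*SAP*

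**What the plan says.** SAP 3.14.2 analyses this secondary endpoint with a Cox model and a Kaplan-Meier curve. The event needs two consecutive results below LOD, or the end of study in place of the second, and is dated to the "first date of achieving viral load below LOD, of the two consecutive timepoints or end of study". The censoring rule is: "Subjects who discontinue early and subject who do not achieve viral load below LOD will be censored". The same sentence fixes the date: they "will be censored at the end of study date reported on the End of Study CRF".

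Viral load is measured on Days 1, 3, 5, 9 and 14 only. Nothing in either document ties the CRF date to the last swab. For the viral load AUC, built from the same swabs, the same SAP section takes the last available assessment as the end of follow-up.

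Two protocol provisions decide how often the two dates differ:

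- Section 7.1.3: "Subjects who discontinue the study early (ie, prior to Day 14) should return to the study site within 24 hours" and no later than 48 hours, for end-of-study procedures. The Schedule of Assessments marks a viral load swab at that visit.
- Section 7.2.2 covers those who do not come: "Site staff will attempt to contact any subject who does not return to the site for the EOS Visit" at least three times, then send a letter. "Any subject who still cannot be reached following those attempts will be considered lost to follow-up". Under Section 7.2, a subject who also withdraws consent to future disclosure has no further evaluations.

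**The concern.** A subject whose last swab was on Day 3, but whose CRF date is after Day 9, sits in the risk sets at Days 5 and 9 with no possibility of an event. The analysis treats that as observed failure to clear. The estimated hazard at each such visit is too low, and so is the clearance curve. If these subjects are more frequent in one arm, the hazard ratio moves as well.

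There is a separate problem of wording. The sentence names two groups to be censored: early leavers, and subjects who do not clear. Read literally, a subject below LOD on Days 3 and 5 who then leaves is censored, although the event definition has been met. Two programmers could derive different data from it.

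**Working it through.** **Inputs from the documents.** Swab days as above, about 35 subjects per arm and 20% dropout (Protocol 11.2). The plan sizes nothing on this endpoint. Its sizing of the primary endpoint reproduces: Welch power is 80.6% at 27 per group, and 27/0.8 = 33.75, so 34 against the stated 35 or so.

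**Assumptions.** True clearance F = 5%, 20%, 55%, 85% by Days 3, 5, 9, 14. Leavers clear at the same rate as others and have no end-of-study swab. Their last swab is equally likely to be Day 1, 3, 5 or 9, so at 20% dropout each group is 5% of subjects. One below-LOD result counts as the event, which is simpler than the planned confirmed event.

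**Step 1: true visit hazards**, h = (F at this visit − F at previous visit)/(1 − F at previous visit):

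0.05/1 = 0.050; 0.15/0.95 = 0.158; 0.35/0.80 = 0.4375; 0.30/0.45 = 0.667.

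**Step 2: CRF date passes one unswabbed visit (20% dropout).** At Day 14 the completers at risk are 0.80 × 0.45 = 0.360. Leavers last swabbed on Day 9 and not cleared add 0.05 × 0.45 = 0.0225. Events are 0.360 × 0.667 = 0.240. The estimated hazard is 0.240/0.3825 = 0.627 instead of 0.667. The same step at Days 3, 5 and 9 gives 0.0475, 0.1496 and 0.4132. Clearance by Day 14 is then

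1 − 0.9525 × 0.8504 × 0.5868 × 0.3725 = 82.3%.

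**Step 3: CRF date passes all remaining visits.** Nobody is censored before Day 14, so Kaplan-Meier equals the observed proportion:

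0.80 × 0.85 + 0.05 × (0 + 0.05 + 0.20 + 0.55) = 0.68 + 0.04 = 72.0%.

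**Step 4: Day 14 clearance under each rule.**

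| Leaving without an end-of-study swab | Last-swab censoring | CRF date passes 1 visit | 2 visits | All remaining |
|---|---|---|---|---|
| 10% | 85.0% | 83.8% | 81.9% | 78.5% |
| 20% | 85.0% | 82.3% | 78.4% | 72.0% |

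**Step 5: hazard ratio (active to placebo).** Simulated Cox models, 35 per arm, 600 runs per scenario, Efron ties, no covariates, CRF date 5, 9 or 14 days after the last swab:

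| True HR | Dropout placebo/active | CRF-date censoring (5, 9, 14 days) | Last-swab censoring |
|---|---|---|---|
| 1.0 | 20%/20% | 1.00, 1.01, 1.01 | 0.99 to 1.01 |
| 1.0 | 30%/10% | 1.13, 1.26, 1.35 | 1.01 to 1.02 |
| 1.0 | 10%/30% | 0.91, 0.80, 0.73 | about 1.00 |
| 1.5 | 20%/20% | 1.45, 1.44, 1.37 | 1.46 to 1.51 |

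With a gap of 2 days or less the two rules agree within simulation error. For example, at 20% dropout, null HR and a 2-day gap, placebo clearance is 84.9% against 85.1%.

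**The case against.** The strongest reply is that the protocol largely prevents the gap. Early leavers are asked back within 48 hours, home visits are allowed, and a swab is part of the visit. A completer who never clears has a CRF date near Day 14, when the last swab is due. A reader might infer from the censoring sentence that early leavers in general bias the analysis. The documents do not support that: the problem is confined to subjects with no end-of-study swab whose CRF date passes a swab day.

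Nor do the documents say which date a site enters for a lost subject. If it is the last visit, the gap disappears. If it is the last contact, the gap may be short. That makes the bias conditional, but it leaves the SAP depending on an unstated convention.

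A reader might also infer that the rule will create a treatment effect. The null hazard ratios of 1.13 to 1.35 need an assumed 30%/10% split, and the documents give only one overall dropout rate. With equal dropout the null ratio holds. At a true ratio of 1.5 the largest shift is ln(1.486/1.369) = 0.08. With about 70 × 0.72 = 50 events the standard error of the log hazard ratio is about 2/√50 = 0.28, so the shift is under a third of one standard error.

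On the wording, the natural reading is that a subject who met the event definition keeps the event. This is an ambiguity to remove, not a demonstrated error.

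**Conclusion.** The point holds for subjects who leave without an end-of-study swab and whose CRF date runs past a scheduled swab day. For them the rule counts unobservable time as event-free and biases the Kaplan-Meier clearance estimate down.

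At 20% such leavers, Day 14 clearance falls from 85% to between 82% and 72%; at 10%, to between 84% and 78.5%. The lower ends are upper bounds on the bias for the assumed timing of last swabs, not expected values: the planned 20% is dropout of every kind, and many of those subjects should have an end-of-study swab. Clearance rates, leaving times, gap lengths and arm-specific dropout are assumptions, and the single-result event means the figures illustrate the planned endpoint rather than describe it exactly.

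The hazard ratio is materially affected mainly when such leavers are unequal between arms. This is one secondary endpoint. The primary endpoint, the sample size, the viral load AUC and the visit-wise proportions below LOD do not use this rule.

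**What to change.** Replace the censoring sentence in SAP 3.14.2 with: *Subjects who have not met the event definition will be censored at the date of their last valid viral load swab (at first dose if there is no post-baseline swab). Subjects who met the event definition before discontinuing count as events.*

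Also state whether a single below-LOD result at an early leaver's last swab counts as an event under the end-of-study alternative in the event definition.

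The cost is a small edit to one SAP paragraph and one dataset derivation. Protocol 11.1 allows SAP changes before unblinding. If every leaver attends the end-of-study visit on time, the results hardly change.
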